1.2 Number of Subjects

A total of 24 (4 subjects per sequence) healthy female and male subjects, balanced by gender and race/ethnicity to the extent possible, who satisfy all of the inclusion criteria (and none of the exclusion criteria), as well as all screening evaluations, before enrollment in the study, will be included in the study. If needed and agreed upon by SKLSI and investigator, replacement subjects will be assigned to the same treatment sequence as the subject they are replacing in order to have at least 15 subjects completing all three treatments,

The number of subjects to be enrolled was chosen based on practical considerations and is considered sufficient for the study objectives. No formal sample size calculation was performed. Subjects who do not complete all the treatments and assessments specified in this protocol may be replaced.

2 STUDY OBJECTIVES AND ENDPOINTS

2.1 Objectives

2.1.1 Primary Objectives

- To assess relative bioavailability of 200 mg of cenobamate given as an oral tablet vs 200 mg of cenobamate given as an oral suspension in fasting condition
- To assess the effect of food on the bioavailability of a 200 mg oral dose of cenobamate given as a suspension

The primary PK objectives are discussed in further detail in the CPAP.

2.1.2 Secondary Objectives

To assess the safety and tolerability of a single 200 mg dose of cenobamate given as either an oral tablet in fasting condition or an oral suspension in fasting and fed condition.

2.2 Endpoints

2.2.1 **Primary Endpoints**

PK parameters will be calculated for cenobamate from plasma data. PK endpoints will be defined in the CPAP.

2.2.2 Secondary Endpoints

- 1. Adverse events (AEs)
- 2. Safety laboratory tests (including clinical chemistry, hematology, coagulation and urinalysis)
- 3. Vital signs (systolic and diastolic blood pressure, pulse rate, respiratory rate, and body temperature)
- 4. Physical examination
- 5. Columbia-Suicide Severity Rating Scale (C-SSRS) score.

3 ANALYSIS POPULATIONS

3.1 Safety Population

The safety population includes all subjects who are randomized and receive at least 1 dose of cenobamate.

3.2 Pharmacokinetic Population

All subjects who have received one dose of cenobamate and have sufficient quantifiable PK samples to calculate primary PK parameters appropriately. The final decision to include subjects in the PK population set takes into consideration possible AEs affecting the disposition of cenobamate (e.g., vomiting or diarrhea). Reasons supporting each decision will be clearly stated in the clinical study report. A sensitivity analysis may be performed if deemed necessary to support a subject's exclusion or inclusion.

4 STATISTICAL METHODOLOGY

4.1 Subject Disposition

The number and percentage of subjects in the study populations (Safety and PK) will be summarized by sequence and overall.

The number and percentage of subjects who enter, complete and prematurely discontinue from the study as recorded on the termination pages of the eCRF will be summarized (number and percentage) by sequence and overall.

Screen failure subjects (i.e.; subjects screened but not randomized) and the associated reasons for failure, inclusion (not met) and exclusion (met) criteria will be listed. A listing of subjects who prematurely discontinued will be provided. A data listing of subject disposition, study completion status, and reason for study discontinuation will also be provided. Table and listings for disposition will be provided for all randomized subjects.

4.2 **Protocol Deviation**

Protocol deviations for all randomized subjects will be captured in a log by the project manager, exported into a clinical dataset, and presented in a data listing.

The number and percentage of subjects with any protocol deviation will be tabulated for each type of deviation (Major/Minor and overall) by sequence and overall. A listing of all protocol deviations will also be provided for all randomized subjects.

4.3 Demographics and Other Baseline Characteristics

Demographic parameters (age; race; ethnicity; sex), baseline characteristics (weight; height; and body mass index[BMI]) will be summarized descriptively by treatment sequence and overall for the Safety population. Continuous variables will be summarized by number of subjects and mean, standard deviation (SD), median, minimum, and maximum values. Categorical variables will be summarized by number and percentage of subjects.

A data listing will be presented for all demographic and other baseline characteristics data.

4.4 Medical History

Abnormalities collected in subjects' CRF pages of medical and surgical histories will be coded using the Medical Dictionary for Regulatory Activities (MedDRA), version 23.0. The number and percentage of subjects with abnormalities in each system organ class (SOC) and preferred term (PT) will be summarized overall for the Safety Population.

4.5 Prior and Concomitant Medications

Prior medication is defined as any medication taken before the date of the first dose of IP. *Concomitant* medication is defined as any medication taken on or after the date of the first dose of IP.

SKLYKP3089		SK Life Science, Inc.
SKLYKP3089C037	Statistical Analysis Plan	Page 16

The use of *prior* and *concomitant* medications will be summarized for the Safety Population by the number and percentage of subjects overall for prior medications, and by sequence and overall for concomitant mediations. If a subject took a specific medication multiple times or took multiple medications within a specific therapeutic class, the subject would be counted only once for the coded drug name or therapeutic class.

World Health Organization (WHO) Drug Dictionary (WHODrug Global B3 Mar2020 version), will be used to classify prior and concomitant medications by therapeutic class and drug name.

4.6 Pharmacokinetic Analysis

4.6.1 Plasma Drug Concentrations and Pharmacokinetic Parameters

The individual plasma drug concentration versus time profiles will be presented using the actual sampling times whereas the mean plasma drug concentration versus time profiles will be presented using the nominal sampling times. Descriptive statistics, N (number of datapoints available), arithmetic mean, median, arithmetic coefficient of variation (%CV), SD of the mean, geometric mean, geometric %CV, minimum value observed, and maximum value observed, will be calculated for plasma drug analyte concentrations at each individual time point for cenobamate.

PK parameters will be calculated using a non-compartmental approach. The primary PK endpoints will include AUC from 0 to infinity (AUC_{∞}) , area under the concentration versus time curve (AUC) from 0 to the last time point with a concentration above the lower limit of quantitation (AUC_{last}), and maximum observed drug concentration (C_{max}) for cenobamate. These parameters will be derived for all treatments received by each subject.

Further PK endpoints for cenobamate as the data permits will include the following: terminal half-life ($t_{1/2}$), time to maximum cenobamate plasma concentration (t_{max}), oral clearance (CL/F), terminal rate constant (λ_z), apparent volume of distribution during terminal phase (Vz/F), and last observed cenobamate plasma concentration (C_{last}).

Refer to CPAP for description of summary statistics for the primary and further PK endpoints.

4.6.2 Statistical Analysis of Pharmacokinetic Data to Assess Formulation Effect

For the evaluation of the formulation effect on cenobamate PK, an analysis of variance (ANOVA) model will be used and the differences between test and reference treatments for AUC_{∞} , AUC_{last} , and C_{max} of cenobamate will be estimated (test and reference treatments are outlined below in Table 3). The PK parameters will be logarithmically transformed prior to analysis and the ANOVA models will include treatment, sequence, and period as fixed effects, and subject nested within sequence as a random effect. From this model, the difference and 90% confidence limits between the test and reference treatments on the log scale will be exponentiated to present the estimates of the geometric mean ratio and associated 90% confidence limits. The absence of a formulation effect will be concluded if the 90% CIs lie within the reference range of [0.80-1.25]. No adjustments will be made for multiplicity.

The following SAS pseudo code will be used:

```
proc mixed data=dataset;
by parameter;
class treatment sequence period subject;
model ln aval = treatment sequence period / ddfm=kr;
random subject (sequence);
estimate "BioAv Trt B (Test: Suspension Fasted) vs Trt A (Ref: Tablet Fasted)"
      treatment -1 1 0 / cl alpha=0.1;
run;
```

A forest plot of the geometric LS mean ratios of AUC_{0-∞}, AUC_{0-last}, and C_{max} of cenobamate will be provided for a visual representation of the data. A single plot will be provided for the test versus reference formulation comparison, with all PK parameters on the plot.

In addition, Wilcoxon signed-rank tests will be used to test for the differences in t_{max} .

The following SAS pseudo code may be used for the Wilcoxon signed-rank test for each treatment comparison:

```
data data2;
set data1;
diffBA= TRTB – TRTA;
run;
ods output TestsForLocation=Tests(where=(test='Signed Rank'));
proc univariate data= data2;
var diffBA;
run;
```

4.6.3 Statistical Analysis of Pharmacokinetic Data to Assess Food Effect

The food effect will be assessed from the same ANOVA model as in section 4.6.2, with the specific contrasts as indicated in the SAS pseudo code below.

proc mixed data=dataset;

```
by parameter;
class treatment sequence period subject;
model ln aval = treatment sequence period / ddfm=kr;
random subject (sequence);
estimate "BioAv Trt C (Test: Suspension Fed) vs Trt B (Ref: Suspension Fasted)"
      treatment 0 -1 1/cl alpha=0.1;
```

```
run;
```

A forest plot of the geometric LS mean ratios of AUC_∞, AUC_{last}, and C_{max} of cenobamate will be provided for a visual representation of the data. A single plot will be provided for the test versus reference food effect comparison, with all PK parameters on the plot.

In addition, Wilcoxon signed-rank tests will be used to test for the differences in t_{max} for the food effect.

The following SAS pseudo code will be used for the food effect comparison:

```
data data2;
set data1;
diffCB = TRTC - TRTB;
run;
ods output TestsForLocation=Tests(where=(test='Signed Rank'));
proc univariate data= data2;
var diffCB;
run;
```

 Table 3:
 Test Treatment and Reference Formulation Treatment for ANOVA Analysis

Assessment	Test Treatment	Reference Treatment				
Bioavailability ^a	Oral Suspension administered under fasted conditions	Oral Tablet administered under fasted conditions				
Food Effect	Oral Suspension administered under fed conditions	Oral Suspension administered under fasted conditions				

^a Bioavailability is assessed for treatments administered under fasting conditions

5 EXTENT OF EXPOSURE AND TREATMENT COMPLIANCE

5.1 Extent of Exposure

Study treatment exposure will be summarized by sequence, treatment period, and study day. IP administration dates and times will be provided in a data listing.

5.2 Treatment compliance

There will be no planned table or listing for treatment compliance for this study. Treatment compliance will be seen from the table above and the listing of Investigational Product Dosing Records.

5.3 Meal Record

Details of meal records, such as meal type, date/time of meal, and amount consumed will be listed.

6 SAFETY ANALYSIS

The safety analysis will be performed using the safety population. The safety parameters will include adverse events (AEs), clinical laboratory parameters, vital signs, and electrocardiographic (ECG) assessments. The last non-missing safety assessment before the date of first dose of study treatment will be used as the baseline for all analyses of that safety parameter. Continuous variables will be summarized by the number of subjects and mean, SD, median, minimum, and maximum values. Categorical variables will be summarized by the number of subjects.

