Treatment Administration			X																										
PK Blood Sampling			X	X	X	X	X	X	X	X	X	X	X	X	X	X	X	X	X	X	X	X	X	X	X				
Pharmacogenomic Blood Sampling		X																											
Discharge																				X									
Outpatient Visit																				X	X	X	X	X	X ⁱ	X			

Note: C-SSRS= Columbia Suicide Severity Rating Scale; AE = adverse event; BMI = body mass index; ECG = electrocardiogram; FSH = follicle stimulating hormone; h = hour; PK = pharmacokinetic

^a Review Inclusion/Exclusion on Day -1

^b Baseline “Baseline/Screening” version of C-SSRS will be used

^c “Since Last Visit” version of the C-SSRS will be used

^d Randomization to occur prior to dosing on Day 1.

^e Pregnancy testing for female subjects of childbearing potential only; postmenopausal women with last menses less than one year will have a serum pregnancy and FSH test during screening only

^f Postmenopausal women only, including women with last menses less than one year

^g Complete physical examination at Screening; Symptom-oriented physical examination on Day 1, Day 22, Day 43 and at follow-up

^h Vital signs (supine systolic and diastolic blood pressure, pulse rate, respiratory rate, and body temperature) measurement in supine position (at least 5 minutes).

ⁱ Note that Visit 17 only is an outpatient visit while Visit 7 and 12 are CRU admission days to bridge between periods

^j Visit 2 is baseline visit Visits 7 and 12 are the start of periods 2 and 3 respectively

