6.3 Vital Signs

Descriptive statistics for actual values and changes from Baseline for vital signs (systolic and diastolic blood pressures, heart rate, respiratory rate, and temperature in supine position) will be summarized at Screening visit (Days -28 to -2), pre-dose on Day 1, post-dose on Days 4, 6, 9, 12, 16, 20 of each treatment period and Day 69 (end of study).

The actual values of vital signs, date of collection/time, reference ranges, and clinical significance will be listed for each scheduled visit.

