8.2 Study Day and Baseline

Study Day is relative to treatment start date;

If analysis date \geq treatment start date,

Day = analysis date - treatment start date +1

Day 1= treatment start date

If analysis date \leq treatment start date,

Confidential and Proprietary, SK Life Science, Inc.

Day = analysis date - treatment start date +1

Day -1= day before treatment start date

There is no Day 0.

Baseline value is defined as the last available value collected before the first dose date of investigational product for all safety laboratory, safety ECG, and vital sign values, unless otherwise specified.

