8.3 Data Handling Conventions

8.3.1 Repeated or Unscheduled Assessments of Safety Parameters

If a subject has repeated assessments before the start of the first treatment, the results from the final nonmissing assessment made prior to the start of the IP will be used as baseline. If a subject has repeated postbaseline assessments for that time point, the last nonmissing postbaseline assessment window will be used.

However, all assessments will be presented in the data listings.

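### The SAP gives two conflicting vital-sign baselines: Sections 6 and 8.2 cut at the date of first dose, which shuts out the Day 1 pre-dose reading, while Section 8.3.1 can be read to select it

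*SAP*

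**What the plan says.** SAP Section 6 sets the general rule for the safety analysis: "The last non-missing safety assessment before the date of first dose of study treatment will be used as the baseline for all analyses". It carries no exception.

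SAP 8.2 gives the same cut, the last available value "before the first dose date of investigational product for all safety laboratory, safety ECG, and vital sign values", but adds that another rule may be specified elsewhere. It also fixes the day count: "Day 1= treatment start date".

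SAP 8.3.1, on repeated or unscheduled safety assessments, uses a different cut. Its condition is "If a subject has repeated assessments before the start of the first treatment", and its rule is that "the results from the final nonmissing assessment made prior to the start of the IP will be used as baseline".

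SAP 6.3 plans "Descriptive statistics for actual values and changes from Baseline for vital signs". Its time points are Screening and then "pre-dose on Day 1, post-dose on Days 4, 6, 9, 12, 16, 20 of each treatment period and Day 69". It defines no vital-sign baseline of its own.

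In the schedules (Protocol Table 4, SAP Table 2), vital signs before the first dose appear at Screening and on Day 1, with no mark for Day -1. The visit description in Protocol 7.1.1.2 agrees. Protocol 12.1 and 12.1.3 place the pre-dose reading within 2 hours of dosing. A footnote to both schedules says that "Visit 2 is baseline visit".

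**The concern.** A cut at the calendar date treats everything collected on the dosing day alike, whether before or after the dose. For vital signs this matters, because the one reading designed to sit immediately before the first dose is taken on that day. Under Sections 6 and 8.2 it is too late to be baseline, and the rule falls back to a Screening reading whose age differs from subject to subject. Screening vital signs also feed exclusion criterion 1 (Protocol 8.2), so that reading has been through an eligibility check.

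Section 8.3.1 can be read to give the other answer. Two programmers working carefully from the same SAP could therefore derive different baselines for the same subject. Vital signs are a named secondary endpoint and change from baseline is part of their planned summary, so the plan should settle this before database lock.

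**Working it through.** The plan states no figure to reproduce. The check applies each rule to the scheduled assessments before the first dose.

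**Inputs**
- Screening: Days -28 to -2 (Protocol Table 4, SAP Table 2).
- First dose: Day 1, with no Day 0 (SAP 8.2).
- Vital signs before first dose: Screening and Day 1 pre-dose (Protocol 7.1.1.1, 7.1.1.2).
- Laboratory tests and ECG before first dose: Screening and Day -1 (same sections). Coagulation is budgeted at Screening only (Protocol Table 9).
- Post-dose vital-sign days (Protocol 12.1): 4, 6, 9, 12, 16, 20; 25, 27, 30, 33, 37, 41; 46, 48, 51, 54, 58, 62; and 69.
- Parameters in SAP 6.3: systolic and diastolic pressure, heart rate, respiratory rate and temperature, which makes 5.

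**Scheduled baseline under each cut**

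| Parameter | Before the date of first dose | Before the date and time of first dose |
|---|---|---|
| Vital signs | Screening | Day 1 pre-dose |
| Laboratory tests | Day -1 (coagulation: Screening, per Table 9) | the same |
| ECG | Day -1 | the same |

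Only vital signs depend on the choice. An unscheduled reading between Screening and Day 1, which Protocol 12.1.3 permits, would replace Screening under the date cut.

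**Age of the vital-sign baseline at first dose**
- Date cut: with no Day 0, Day -28 is 28 days before Day 1 and Day -2 is 2 days before. The range is 2 to 28 days, so subjects can differ by 28 - 2 = 26 days.
- Date-and-time cut: at most 2 hours.

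**Interval from baseline to post-dose readings**
- Day 4 is 4 - 1 = 3 days after Day 1. From Screening it is 2 + 3 = 5 to 28 + 3 = 31 days. This is the time point where the two rules differ most in relative terms.
- The last Period 1 reading, Day 20, is 19 days after Day 1 and 21 to 47 days after Screening.
- The first post-dose reading of Period 2, Day 25, is 25 - 1 = 24 days after Day 1. Day 69 is 69 - 1 = 68 days after.
- There are 6 + 6 + 6 + 1 = 19 post-dose time points. Of these, 6 lie in Period 1 and 13 lie in Periods 2 and 3 or on Day 69. The 13 are 24 to 68 days from baseline even under the date-and-time cut.

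**Number of summaries touched**
- 5 parameters x 19 time points = 95 post-dose change summaries. This counts table cells and says nothing about bias. It leaves out the pre-dose readings on Days 22 and 43, which SAP 6.3 may or may not intend to include.

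**Comparison between treatments**
- For a subject with baseline b and readings Y under treatments A and B, (Y_A - b) - (Y_B - b) = Y_A - Y_B. The baseline cancels, so mean differences between treatments in complete data are the same under either rule.

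**The case against.** The strongest reply is that the SAP already contains the right rule. Section 8.2 yields to other specifications, and Section 8.3.1 supplies one. On a plain reading, every subject who follows the schedule has two vital-sign assessments before first treatment, so 8.3.1 applies to all of them and picks Day 1 pre-dose. Part of this stands: it cannot be said that the SAP as a whole discards the Day 1 reading as baseline. But 8.3.1 sits under a heading on repeated or unscheduled assessments, and its next sentence concerns repeats at one time point, so a narrower reading is equally open. Section 6 allows no exception at all. The reply therefore turns an apparent error into a conflict and does not remove it.

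A reader might also infer from SAP 6.3 that the Day 1 pre-dose reading will be reported as a change from Screening, giving five changes before any drug is given. The text does not establish that. Section 6.3 uses one list of time points for actual values and for changes, and the list includes Screening. Section 6.2 is drafted the same way and lists Day -1, the scheduled baseline for most laboratory tests. Appearing in the list does not show that a time point is not the baseline.

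Two further supports are weak. The footnote on Visit 2 labels a visit that runs from Day -1 to Day 4 and is not a derivation rule. The eligibility argument is unquantified, since values outside the normal range are acceptable if the investigator judges them not clinically significant.

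Finally, the Day 1 pre-dose values are still summarized and listed with their times, so a reader could recover the other change from the listings. That limits the harm, but the planned tables would still be ambiguous.

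**Conclusion.** The SAP gives two vital-sign baselines that cannot both be followed. Sections 6 and 8.2, read literally, give Screening, 2 to 28 days before the first dose. Section 8.3.1, on a reasonable reading, gives Day 1 pre-dose, within 2 hours of it. The documents do not support the stronger claim that the Day 1 reading is definitely excluded.

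The impact is minor. It reaches only descriptive changes from baseline in vital signs, and most of the gain from a later baseline falls in Period 1. The primary PK analysis, laboratory baselines, ECG listings and complete-data mean differences between treatments are unaffected. SAP 6.3 plans no vital-sign test, threshold or shift table.

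This rests on scheduled assessments being done as planned, with no unscheduled reading between Screening and Day 1. The documents give no vital-sign variability, so the shift in measured units is not estimated.

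**What to change.** Use one rule in SAP 6, 8.2 and 8.3.1: baseline is the last non-missing value before the date and time of first dose. Period 1 Day 1 pre-dose then becomes the vital-sign baseline, and an earlier reading serves only if it is missing. In SAP 6.3, state that changes from Baseline start after that reading.

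The cost is a line of wording in three sections and a clarification in a fourth. No new data or tables are needed: SAP 5.1 already lists dosing dates and times, and SAP 6.3 already lists vital-sign collection times. Laboratory and ECG baselines do not move under the new wording.

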6.1 Adverse Events

Adverse events will be coded by system organ class and preferred term using the MedDRA, Version 23.0.

Treatment-emergent AEs (TEAEs) are defined as AEs that start or worsen (increase in severity) on or after the first dose date of study medication (Day 1) to the follow-up visit (Day 69).

If more than 1 AE is coded to the same preferred term for the same subject, the subject will be counted only once for that preferred term using the greatest severity and strictest causality for the summarization by severity and causal relationship.

Related TEAEs include all those classified by the investigator as having a possible, probable, or definite relationship to the Investigational product. Unrelated TEAEs are those events classified as unrelated or having a remote likelihood of being related to the Investigational product. If the same event occurs more than once per subject and treatment, and there is more than 1 relationship classification, the most related value will be summarized. For summaries by severity, the most severe grade will be selected.

The number and percentage of subject with TEAEs by system organ class and preferred term, and by severity, and by causal relationship to the IP, will be summarized by treatment and overall.

A listing of all AEs, along with SAEs, AEs leading to death, and AEs leading to discontinuation of IP will be provided.

The MedDRA version will be specified in a footnote in both tables and data listings.

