10.5.1.2. Timing of Doses for Treatment C

- The study drug will be orally administered to subjects in the morning approximately 30 minutes after the start of a high-calorie, high-fat meal.
- The study drug will be swallowed together with 240 mL tap water (room temperature). The study drug should be swallowed whole.
- Administration of the study drug will be supervised by the Investigator or designee. After drug administration, a mouth and hand inspection will take place.
- A lunch and dinner will be served approximately 4 hours and 10 hours post-dose, respectively.

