12.2.1.4. Causality Assessment

An assessment should be made of the causal relationship of the adverse event to the study treatment, i.e., according to the following definitions in [Table 11](#).

Table 11: Definitions of Causality Assessment

Causality Assessment	Definitions
Unrelated	The event is occurring before dosing The event is definitely produced by the subject's clinical state or by other modes of therapy administered to subject
Remote	The event does not follow a reasonable (poor) temporal relationship with drug treatment And/or the event is readily explained by the subject's clinical state or by other modes of therapy administered to subject
Possible	Reasonable temporal relationship with drug treatment But the event could have been produced by the subject's clinical state or by other modes of therapy administered to subject
Probable	Reasonable temporal relationship with drug treatment, abates upon discontinuation of drug And/or event cannot be reasonably explained by the known characteristics of the subject's clinical state.
Definite	Distinct temporal relationship with drug treatment, abates upon discontinuation of drug (de-challenge) and is confirmed by reappearance of the reaction on repeat exposure (re-challenge)

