12.4. Recording Adverse Events

Adverse events spontaneously reported by the patient/subject and/or in response to an open question from the study personnel or revealed by observation will be recorded during the study at the investigational site. Clinically significant changes in laboratory values, blood pressure, and pulse need not be reported as AEs. However, abnormal values that constitute an SAE or lead to discontinuation of administration of study drug must be reported and recorded as an AE.

Information about AEs and SAEs will be collected from the first administration of study drug through the follow up visit. The AE term should be reported in standard medical terminology when possible. For each AE, the investigator will evaluate and report the onset (date and time), resolution (date and time), intensity, causality, action taken, serious outcome (if applicable), and whether or not it caused the patient to discontinue the study.

It is important to distinguish between serious and severe AEs. Severity is a measure of intensity whereas seriousness is defined by the criteria under Section 12.2. An AE of severe intensity may not be considered serious.

Should a pregnancy occur in a subject or a male subject’s partner, it must be reported and recorded on SKLSI’s pregnancy form. Pregnancy in itself is not regarded as an AE unless there is a suspicion that an investigational product may have interfered with the effectiveness of a contraceptive medication.

The outcome of all pregnancies (spontaneous miscarriage, elective termination, normal birth or congenital abnormality) must be followed up and documented even if the patient was discontinued from the study.

All reports of congenital abnormalities/birth defects are SAEs. Spontaneous miscarriages should also be reported and handled as SAEs. Elective abortions without complications should not be handled as AEs.

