13.2.3. Adverse Events

Adverse events will be coded using the Medical Dictionary for Regulatory Activities (MedDRA). MedDRA terms will be used to summarize AEs by system organ class (SOC) and preferred term (PT).

Treatment-emergent adverse events (TEAEs) are defined as adverse events that were started or worsened on or after the date of the first dose of study medication (Day 1) to the follow-up visit (Day 69).

A listing of all individual AEs will be provided. Summary tables of TEAEs will be presented by SOC and PT, including a table containing the number of subjects experiencing AEs by treatment group, and a table containing the number of subjects experiencing SAEs by treatment group (if applicable). Details of the AE summary analyses will be described in Statistical Analysis Plan (SAP).

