8.3.4 Missing Causal Relationship to study drug for Adverse Events

If the causal relationship to the study treatment is missing for an AE that started on or after the date of the first dose of study treatment, a causality of yes will be assigned. The imputed values for causal relationship to study treatment will be used for the incidence summary; the values will be shown as missing in the data listings.

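### TEAEs are cut at the calendar date of the first dose, so a symptom starting on Day 1 before dosing counts as treatment-emergent although onset and dosing times are recorded (minor)

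*SAP*

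**What the plan says.** **Definition.** SAP 6.1 sets the TEAE window as "on or after the first dose date of study medication (Day 1) to the follow-up visit (Day 69"). Protocol 13.2.3 has the same boundary: events that "started or worsened on or after the date of the first dose of study medication (Day 1"). No other section of either document removes Day 1 onsets that precede the dose. SAP 6.1 then summarizes TEAEs by treatment and overall.

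**Times available.** Protocol 12.4 requires that "the investigator will evaluate and report the onset (date and time), resolution (date and time") be recorded for each AE. Protocol 11.1 records the clock time of dosing, SAP 5.1 lists dosing dates and times, and SAP 5.3 lists meal times.

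**What precedes the dose on Day 1.** Vital signs may be taken up to 2 hours before dosing (protocol 12.1 and 12.1.3), and the pre-dose PK sample within 30 minutes before it (protocol Table 6). Treatment C is given "approximately 30 minutes after the start of a high-calorie, high-fat meal" (protocol 10.5.1.2).

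**Causality and imputation.** Under Unrelated, protocol Table 11 lists "The event is occurring before dosing". SAP 8.3.4 gives this rule for absent causality ratings: "for an AE that started on or after the date of the first dose of study treatment, a causality of yes will be assigned". SAP 8.3.3 uses the same date boundary to impute missing severity as severe.

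**The concern.** A treatment-emergent event should follow exposure. On Day 1 there is a pre-dose interval in which subjects are stuck with a needle and, for some, eat a heavy breakfast. A complaint that starts then cannot be caused by cenobamate, yet the definition puts it in the TEAE tables.

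Those tables are the main output for the secondary objective, safety and tolerability of the tablet fasted and the suspension fasted and fed. With 24 subjects, one wrongly counted subject is visible in a percentage. The imputation rules add a small internal contradiction: an unrated pre-dose Day 1 event would be tabulated as related, while the protocol's own causality table would call it unrelated.

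**Working it through.** The documents give no figure to reproduce, because the point concerns a definition. The check applies both cuts to example onsets and counts the subjects whom the meal example can affect.

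**Step 1. Date cut against date-time cut.** Assume a first dose at 09:00 on Day 1; the clock time is illustrative and does not affect the result.

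| Onset | TEAE by date (as written) | TEAE by date and time |
|---|---|---|
| Day -1, evening | No | No |
| Day 1, 2 h before dose | Yes | No |
| Day 1, during meal, 20 min before dose | Yes | No |
| Day 1, 1 h after dose | Yes | Yes |
| Day 22, during meal, 20 min before dose | Yes | Yes |

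The two rules differ only for Day 1 onsets before the dose. Before the dose on Day 22 or Day 43 a subject has already received cenobamate, so the flag is the same under either rule.

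**Step 2. Who is affected.** The general pre-dose interval on Day 1 applies to all 24 planned subjects. The meal falls on Day 1 only where Treatment C comes first: sequences 3 (C, A, B) and 4 (C, B, A) in protocol Table 3. With 4 subjects per sequence (protocol 7.2), 2 × 4 = 8 of 24. For the other 24 − 8 = 16 the meal is on Day 22 or Day 43.

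**Step 3. Size per subject.** If 24 subjects are dosed with a treatment, one additional subject with a TEAE adds 1/24 = 4.2 percentage points. This is a maximum, because SAP 6.1 counts a subject once per preferred term: someone already counted in a row adds nothing to it. The 24 is an assumption. Replacement aims for at least 20 completers in protocol 7.2 and at least 15 in SAP 1.2. If the denominator fell to those numbers, the step would be 1/20 = 5.0 or 1/15 = 6.7 points.

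**Step 4. Are these events collected?** Protocol 12.1.1 records AEs from Screening and 12.5.1 from signing of consent, and SAP 8.3.3 has a rule for AEs before the first dose. Protocol 12.4 instead starts collection at the first administration. Three places point to collection and one points against it. On the 12.4 text, pre-dose events would not reach the database as AEs.

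**Step 5. Imputation.** For an unrated symptom starting on Day 1 before dosing, SAP 8.3.3 gives severe and SAP 8.3.4 gives related. Under a date-time cut, SAP 8.3.3 would give mild, the related imputation would not apply, and the event would not be in the TEAE tables.

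**The case against.** The strongest reply is that a date cut is a common, deliberately inclusive convention. It is the same in protocol and SAP, it matches the date-based baseline in SAP 6 and 8.2, and it feeds descriptive tables with no test or decision rule. All AEs are listed, so a reader can identify a pre-dose onset. Protocol 12.4 asks for intensity and causality on every AE, so missing ratings should be rare, and a rated pre-dose event is unrelated under Table 11 and stays out of the related summaries. All of this stands, and it is why the point is minor. It does not justify a date cut where the times are already recorded.

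A reader might infer more than the documents support:

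- **That the fed treatment is broadly biased.** Only the roughly 30 minutes from the start of the meal to the dose is specific to Treatment C, and it changes the TEAE flag for only 8 of 24 subjects. Complaints before the meal can arise under any treatment. Many meal complaints would start after the dose and remain TEAEs. Treatment C is itself defined as the suspension under fed conditions.
- **That pre-dose examination findings become TEAEs.** Protocol 12.1 sends clinically significant examination findings before the first dose to medical history. For vital signs the text is mixed: 12.4 does not require blood pressure and pulse changes to be reported as AEs, while 12.5.1 does. The point is safest for symptoms.
- **That every such event adds 4.2 points.** It is an upper limit per additional subject, not per event.

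**Conclusion.** The point holds, at minor severity. As written, the definition counts symptoms that precede any exposure as treatment-emergent, and unrated ones would be imputed as severe and related against protocol Table 11. Each additional subject counted adds at most 4.2 percentage points to a treatment's TEAE incidence, assuming 24 subjects dosed. The documents do not allow the number of such subjects to be estimated; the interval is short and the number is probably small.

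The conclusion assumes that AEs are collected before the first dose, as protocol 12.1.1 and 12.5.1 say and 12.4 does not. It does not extend to meals on Days 22 and 43. There the gap is a different one: SAP 6.1 reports by treatment but gives no rule for assigning an AE to a treatment.

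**What to change.** 1. In SAP 6.1 and protocol 13.2.3, define a TEAE as an AE with onset or worsening at or after the date and time of the first dose. If the protocol is not amended, record the difference in SAP section 9, which now reports no changes.
2. Keep Day 1 events with a missing onset time as TEAEs. This also covers partial start dates that SAP 8.3.2.2 sets to the first-dose date, since they carry no time.
3. Use the same cut in SAP 8.3.3 and 8.3.4.
4. State in SAP 6.1 that each TEAE is assigned to the most recent dose by date and time. A complaint during a Day 22 or Day 43 pre-dose meal would then go to the preceding period's treatment; the listing should show its timing relative to the coming dose.
5. Reconcile the start of AE collection in protocol 12.4 with 12.1.1 and 12.5.1.

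The cost is slight: wording changes and a date-time comparison in programming, on data already recorded. The downside is a slightly less inclusive TEAE count.
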